3.3 Primary and secondary study endpoints

Primary endpoints

• Scores on the perceived stress scale at post-intervention (T5) controlling for baseline (T1)

Secondary endpoints

- Performance on the behavioral pattern separation task (post-intervention and follow-up/T6)
- PROMIS depression and anxiety (post-intervention and follow-up)

Tertiary and exploratory endpoints

- Symptoms of PTSD measured using the PCL-5 (post-intervention and follow-up)
- PROMIS sleep disturbances (post-intervention and follow-up)
- Five-facet mindfulness questionnaire, awareness subscale (post-intervention and follow-up)
- NIH toolbox Loneliness (post-intervention and follow-up)
- Healthy Minds Index (post-intervention and follow-up)
- Real-world experiential diversity measured using continuous GPS location tracking (Measured continuously throughout study participation)
- Trajectories of change for self-report outcomes assessed on a weekly basis

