4.0 Number of Participants

4.1 Total number of participants

This study will enroll 150 participants at UW-Madison.

4.2 Number of participants expected to be enrolled and screened vs. number of participants needed to complete the study

N/A - Only eligible participants will be enrolled in this study. Participants will be screened prior to enrollment.

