13.2 Schedule of study procedures

13.2 Schedule of study proce	dures			4-W Interv		
Study Procedure/Activity	Web Screen	Phone/ Zoom Call	T1	T2-T4	T5	Т6
Consent via Information Sheet	X					
Screening Questions	X					
Review Eligibility	X					
Informed Consent Process for		X				
Main Study						
Payment Information Survey		X				
Payment Information Update						X
Survey						
Intervention (i.e., Healthy				X^1	X^1	
Minds Program)						
Behavioral Pattern Separation			X		X	X
Task						
Attention Check Items			X		X	X
Behavioral Risk Factor			X			
Surveillance System (BRFSS)						
Adverse Childhood						
Experiences (ACE) Module						
Demographics			X			
Demographics & Meditation			X			
Experience						
Determinants of Meditation			X			
Practice Inventory-Revised						
(DMPI-R)						
Digital Working Alliance				X^1	\mathbf{X}^1	
Inventory (DWAI)						
Feedback Survey			X	X	X X	X
Five Facet Mindfulness			X		X	X
Questionnaire (FFMQ),						
Awareness Subscale						
Flourishing Measure			X		X	X
Global Physical Activity			X		X	X
Questionnaire (GPAQ)						

Healthy Minds Index		X		X	X
(HMIndex)					
Mainz Inventory of		X		X	X
Microstressors (MIMIS)					
Marlowe-Crowne Social		X			
Desirability Scale (MCSDS)					
Mindfulness-Based Program -				X^1	
Meditation-Related Adverse					
Effects Scale (MBP-MRAES)					
Mindfulness Adherence			X^1	X^1	X^1
Questionnaire (MAQ)					
NIH Toolbox Loneliness		X		X	X
Pre- & Post-Practice Items			X	X	
PROMIS Item Bank -	X	X	X	X	X
Emotional Distress - Anxiety					
(Computer Adaptive Version)					
PROMIS Item Bank -	X	X	X	X	X
Emotional Distress -					
Depression (Computer					
Adaptive Version)					
PROMIS Item Bank -		X	X	X	X
Emotional Distress - Sleep					
Disturbance (Computer					
Adaptive Version)					
Perceived Stress Scale (PSS)		X	X	X	X
PTSD Checklist (PCL-5)		X		X	X
Location Tracking with		X^2	X^2	X^2	X^2
Passive GPS ⁴					
Debriefing Form					X

¹HMP group only

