HMP group participants will be instructed on downloading and installing a study-specific version of the HMP app. The 4-week meditation program will take approximately 60 minutes to complete each week. The program will be self-paced and completed remotely. While completing the HMP each week, participants will listen to podcast-style lessons in the app to learn about meditation from scientists and experts in well-being. The app will also guide participants through seated and active meditations. Participants may have the option to provide demographic and meditation experience information and complete the Healthy Minds Index questionnaire to assess their current level of well-being within the app. The app will collect activity data (e.g., when, how long, and what content was listened to), device type, and GPS data (if enabled by the participant). Participants will also occasionally answer pre- and post-practice questions. The app will not collect any identifying information. Participants will have the option to continue using the HMP app after completing the 4-week program. If they choose to do so, we will continue to monitor their app usage and any other data collected through the HMP app throughout the study to learn more about its long-term impact on well-being. The HMP app is considered an FDA regulated device that should qualify as a "non-significant risk (NSR) device". We are seeking an NSR determination and have, therefore, uploaded an NSR request letter in ARROW (see Drug and Device Documents section, #2 Device Documentation).

Timepoints 2-5 - During & Post-Intervention Activities: HMP group participants will complete online measures (see section **13.2 Schedule of study procedures**) remotely through REDCap for Timepoints 2-5 during the same weeks as the 4-week intervention. The measures will take 10 to 45 minutes to complete each week. Waitlist participants will also complete most of the same measures over 4 weeks. Participants will have approximately one week to complete each set of self-paced activities.

Timepoint 6 - 3-Month Follow-Up: About three months after Timepoint 5, participants will complete a final set of measures (see section **13.2 Schedule of study procedures**) remotely online through REDCap, which will take 30 to 45 minutes.

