20.3 Participant population(s) for analysis

Participants will be assigned to HMP and waitlist groups at a 2:1 ratio.

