20.4 Statistical methods

Group differences for the intervention will utilize linear mixed effects models with a random intercept and slope for each participant to account for non-independence of error and to maximize use of data with missing observations. We will conduct Pearson correlation analyses using difference scores between baseline and post-intervention/follow-up timepoints to test whether reductions in perceived stress are associated with behavioral or imaging outcomes hypothesized to contribute to differences in perceived stress.

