20.6 Handling of missing data

Linear mixed effects analyses account for missing data in a robust manner relative to, e.g., ANOVA. We will use all available observations and do not plan to impute missing data. We will document reasons for missing data, evaluate whether data appear missing at random, and evaluate the impact of missing data using sensitivity analyses based on the nature of missing data.

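### The only covariance in section 20.4, a random intercept and slope, is likely to give too small a standard error for the primary T5 contrast if the slope is linear in weeks over all six PSS visits

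*Combined protocol and SAP*

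**What the plan says.** - **Model.** Section 20.4 plans "linear mixed effects models with a random intercept and slope for each participant to account for non-independence of error". It does not say what the slope is a slope on, whether time is in weeks or visit number, whether fixed time is categorical or linear, or which visits enter. It names no residual correlation, robust standard error, degrees-of-freedom method or fallback.
- **Primary endpoint.** Section 3.3: "Scores on the perceived stress scale at post-intervention (T5) controlling for baseline (T1").
- **Visits.** The table in section 13.2 marks PSS at T1, T2-T4, T5 and T6. Section 13.3 places "Timepoints 2-5 during the same weeks as the 4-week intervention", and for T6 says "About three months after Timepoint 5, participants will complete a final set of measures". With T1 as week 0, PSS falls at about weeks 0, 1, 2, 3, 4 and 17.
- **Data used.** Section 20.6: "We will use all available observations and do not plan to impute missing data". The sensitivity analyses promised there concern missing data, not the covariance.
- **Hypotheses.** Section 3.2 states the group differences at both post-intervention and follow-up. Together with section 20.6, this makes a single model over all six visits the natural reading, although no sentence says so for the primary analysis.

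**The concern.** The issue is the error structure, not the choice of coefficient. It remains even when the T5 arm contrast is coded correctly with a separate mean for each arm and visit.

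A random intercept and slope forces each participant's departure from the group mean to lie on a line, plus independent noise. On a week scale, T6 dominates that line. Suppose a participant's change builds over the four programme weeks and then holds. A line through T1 and T6 would put only 4/17 = 24% of that change at T5. The rest is pushed into a residual variance shared by all visits, so the modelled variance at T5 falls below the true one. Serial correlation between neighbouring weekly scores has a similar effect, because the model has no term for it.

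The primary p-value and confidence interval come from this model. Too small a standard error raises the false-positive rate above the stated 0.05 and narrows the interval on the main result.

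**Working it through.** **The plan's own figure.** Section 4.1: "This study will enroll 150 participants at UW-Madison". Section 20.3: "Participants will be assigned to HMP and waitlist groups at a 2:1 ratio". With the 10% dropout of section 20.2, 100 and 50 become 90 and 45. For d = 0.5, two-sided 0.05 (sidedness is not stated), normal formula:
- 90 vs 45: 0.5/√(1/90 + 1/45) = 2.739; Φ(2.739 − 1.96) = 78.2%.
- 100 vs 50: 0.5/√(1/100 + 1/50) = 2.887; Φ(2.887 − 1.96) = 82.3%.

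The stated 80% reproduces within about 2 points. It is not in dispute and does not involve the covariance.

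**Weight of T6 in a slope.** Weeks 0, 1, 2, 3, 4, 17 have mean 4.5. Squared deviations are 20.25, 12.25, 6.25, 2.25, 0.25 and 156.25, total 197.5. T6 supplies 156.25/197.5 = 79%. With visit numbers 1 to 6, the mean is 3.5 and T6 supplies 6.25/17.5 = 36%. The unstated time scale therefore matters.

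**Method.** The documents give no PSS variances or correlations, so true covariances Σ (total variance about 1) were assumed and varied.
1. Find the intercept-plus-slope covariance V closest in likelihood to Σ, by minimising log|V| + tr(V⁻¹Σ), with categorical visit means by arm.
2. SE ratio r = (T5 standard error under V) / (true standard error of the same estimate).
3. Type I error = 2 × [1 − Φ(1.96 r)]. For r = 0.96: 1.96 × 0.96 = 1.88, giving 6.0%. For r = 0.79: 1.96 × 0.79 = 1.55, giving about 12%.

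**Six visits, slope in weeks, T1 as covariate.**

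| Assumed truth | SE ratio | Type I error |
|---|---|---|
| Plateau after week 4, SD of change 0.3 | 0.965 | 5.9% |
| Plateau, SD of change 0.5 | 0.920 | 7.1% |
| Plateau, SD of change 0.7 | 0.875 | 8.6% |
| Stable trait plus weekly correlation 0.70-0.85 | 0.92-0.93 | 6.8-7.2% |
| Compound symmetry, or change linear to week 17 | 1.00 | 5.0% |

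With T1 treated as an outcome, the same kinds of assumption give 6.1-10.4%.

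**Simulation.** REML fits with a common baseline mean, 100 vs 50, 10% monotone dropout, no true effect, normal reference distribution. Here J is the all-ones matrix, I the identity and g = (0, 0.25, 0.5, 0.75, 1, 1).

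| Assumed Σ | Stated model: SE ratio, type I error | Unstructured: SE ratio, type I error |
|---|---|---|
| Plateau: 0.6J + 0.4gg′ + 0.3I | 0.80, 12.2% | 0.95, 5.7% |
| Autoregressive: 0.4J + 0.4 × 0.8^(weeks apart) + 0.2I | 0.85-0.88, 8.7-9.3% | 0.97, 7.7% |
| Compound symmetry: 0.6J + 0.4I | 0.97, 5.3% | 0.93, 7.3% |

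The stated model had 600-1000 runs per cell and the unstructured model 300, so the latter's Monte Carlo error at 5% is √(0.05 × 0.95/300) = 1.3 points. No small-sample correction was applied. A separate check (90 vs 45, T1 as covariate, 600 trials per scenario) gave 5.7-8.7% for the stated model and 3.8-5.3% for unstructured covariance.

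**Other readings of section 20.4.**
- T1-T5 only: type I error 4.2-5.0%. One exception is an early step change with T1 as an outcome, where the SE ratio was 0.94-0.96.
- Slope on visit number, six visits: type I error 2.3-6.5% under the assumptions behind the 6-12% range, so the error can go either way.

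**Outcomes measured only at T1, T5 and T6** (for example pattern separation and PCL-5). With T1 as a covariate, two visits remain. They give 3 variance and covariance terms for 4 parameters (intercept variance, slope variance, their covariance, residual variance), so the parameters cannot be separated. The 2 × 2 marginal covariance is still determined. In 200 simulated fits (90 vs 45) all returned estimates, and the T5 standard error matched that from ANCOVA at T5 (ratio 1.000). With T1 as an outcome there are 6 terms for 4 parameters.

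**The case against.** The strongest reply is that the criticised model is partly constructed by the reader. Section 20.4 does not say the slope is a straight line in weeks, does not say T6 enters the primary model, and does not fix the mean structure. The primary endpoint concerns T5 and T1 only, and the sentence on using all observations stands in a section about missing data. A primary model on T1-T5 would largely remove the problem. This stands, and it is why the point is conditional. It does not dispose of the point, because the six-visit, week-scale model is the natural reading and nothing in the plan rules it out.

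A reader might infer that the stated model has been shown not to fit PSS. The documents do not support that. They give no PSS variances or correlations, and under compound symmetry or change linear to week 17 the model is correct. An early step change with T1 as a covariate also gives an SE ratio of 1.00.

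A reader might also infer that the model cannot be estimated for the three-visit outcomes. That goes too far. Only the split between random effects and residual is not unique. Some software will warn or refuse, but the T5 contrast and its standard error are identified. Moreover, section 3.3 states baseline control only for the primary endpoint.

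Finally, the gain from unstructured covariance is clear in the plateau simulation but not in the autoregressive one (7.7% against 8.7-9.3%, within Monte Carlo error). Under compound symmetry it brought no gain (7.3% against 5.3%). Those runs lacked the small-sample correction that the fix includes. The separate check, at 3.8-5.3%, is more favourable.

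**Conclusion.** The point holds in conditional form. Section 20.4 offers one covariance and leaves open the choices that decide whether it is adequate. If the slope is linear in weeks over all six PSS visits, with categorical visit means, the T5 standard error is likely to be about 4-20% too small and the type I error about 6-12% instead of 5%, provided individual change levels off after week 4 or weekly scores are serially correlated. Both are plausible for a four-week programme with weekly measurement, but both are assumptions. More extreme assumed covariances reached about 15%; the conclusion does not rest on them.

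The documents do not show that the primary test is anti-conservative as it will actually be run, since that depends on visits and a time scale they do not state. The sample size and the stated power calculation are unaffected. This is a cheap improvement to the analysis, not a demonstrated error in it.

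**What to change.** In section 20.4, for the T5 and T6 group comparisons, specify visit as categorical with an unstructured within-participant covariance and Kenward-Roger or Satterthwaite degrees of freedom. State which visits enter and whether T1 is a covariate or an outcome. If the model does not converge, keep the stated random intercept and slope with sandwich standard errors. Keep the random-slope model for the exploratory weekly trajectories in section 3.3, where a slope is the quantity of interest.

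The change takes a sentence or two. For PSS, covariance parameters rise from 4 to 15 (five outcome visits, 5 × 6/2) or 21 (six visits, 6 × 7/2), which about 135 participants can support. The reported interval may be slightly wider. Enrolment and visits do not change.

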20.5 Planned interim analysis

Given the low risk of the intervention, no interim efficacy or safety analyses are planned.

20.6 Handling of missing data

Linear mixed effects analyses account for missing data in a robust manner relative to, e.g., ANOVA. We will use all available observations and do not plan to impute missing data. We will document reasons for missing data, evaluate whether data appear missing at random, and evaluate the impact of missing data using sensitivity analyses based on the nature of missing data.

21.0 Potential Benefits to Participants

21.1 Potential benefits

Participants may benefit from using the HMP, which is designed to introduce meditation practice as a way of reducing stress and developing greater balance, ease, and fuller participation in life. This meditation training is a way of learning to relate directly to whatever is happening in your life including the challenges of stress, pain, illness, and everyday demands. Waitlist control participants can use the HMP after completion of the study at no cost.

21.2 Direct benefits

There are no direct benefits for participants.

22.0 Risks to Participants

22.1 Risks, discomforts, hazards, or inconveniences

Risk of emotional responses:

Study surveys include questions about mental health that could affect a participant's mood or make them feel embarrassed. Emotional upset due to study participation is a potential but unlikely risk. In our experience from previous studies, it is rare for a participant to find self-report questionnaires to be extremely upsetting.

Risk of location tracking:

GPS location data collected from participants' smartphones could be used to see specific locations that participants have visited and whether participants may have engaged in activities or visited places that are potentially stigmatizing or embarrassing.

Risk of confidentiality breach:

There is a slight risk of breach of confidentiality, which could result in legal implications or stigmatization. There is a chance that concerns about safety (e.g., self harm, possible child abuse) will be discovered during the course of the study, and that these discoveries could require mandatory reporting and place subjects at possible legal risk. There is the risk that information, such as health information or GPS location information, could become known to subjects, doctors, or others. If this happens it may lead to loss of insurance, difficulty obtaining insurance, an increase in premiums, job loss, reduced employability, and harmful psychological effects on the subject.

22.2 Risks associated with delaying standard treatment

N/A

22.3 Procedures that have unforeseeable risks

N/A

22.4 Procedures that have potential risks to an embryo or fetus

N/A

22.5 Risks to others who are not participants

N/A

22.6 Minimizing risks

Minimizing risk of emotional responses:

We will inform participants in the consent form and in survey instructions that some questions may ask about sensitive topics and that they may skip any items that they are not comfortable answering, except for certain required items (e.g., the PSS is required because it is a primary study measure). As stated in the consent form, participants are free to discontinue at any point during the experiment.

If a participant reveals suicidal ideation, self-harm, or intent to harm others, study staff will consult with clinical research personnel. A clinician will contact the participant by phone to assess intent, the level of risk, and provide referrals as needed. In the circumstance that an individual indicates that self-harm or harm to others is imminent, 911 will be called. All interactions regarding suicide risk and referral will be carefully documented and closely tracked by the clinical research personnel. A formal incident report will be filed with the IRB in cases in which a clinician notifies authorities. All participants will be provided with therapeutic resources regardless of their responses.

Minimizing risk of location tracking:

We will inform participants in the consent form about how we will use and protect location data. The FollowMee app will not collect any identifying information. Location data will only be associated with a non-identifiable device ID and subject ID. Data will be stored on secure password-protected servers. Study staff will not view real-time GPS locations, other than to confirm that the FollowMee app is functioning correctly. Data will be encrypted during download, and security measures for the Center for Healthy Minds network will provide protection against data breach. After the data are downloaded, our staff will protect participant confidentiality by not viewing or analyzing the minute-by-minute data, other than for the purpose of conducting quality control checks of these data. When reviewing these data, staff will view lists of latitude/longitude coordinates, and will make no effort to link these coordinates to specific places that could reveal embarrassing, stigmatizing, or illicit information. Data analysis will focus on extracted summary measures across a given day; for example, total distance traveled, number of distinct locations visited, and diversity of locations visited (or "roaming entropy"; see Heller et al., 2020).

Minimizing risk of confidentiality breach:

We will use data storage procedures to reduce the risk of confidentiality breach (e.g., data coding, secure storage, trained personnel). Additionally, although GPS location information will be collected within the GPS application, this application will not have access to any identifiable participant information or other data (e.g., questionnaire responses). This will be made explicitly clear to the participants. Because potential safety concerns (e.g., self harm, possible child abuse) may require mandatory reporting and place subjects at possible legal risk, we will inform participants about this limit to confidentiality in the consent form. Also, this study is funded by

the NIH and has a Certificate of Confidentiality that provides additional confidentiality protections.

23.0 Provisions to Monitor the Data to Ensure the Safety of Participants

23.1 Data and safety monitoring plan

Adverse events will be tracked (including details of the incident, actions taken, and follow-up steps) by study staff and reported to the PI. The PI will be responsible for the monitoring and reporting of adverse events, as necessary, to the IRB.

Other notable incidents that occur during recruitment, consent, or data collection that are determined to be unexpected and related to the study procedures will be reported in a detailed log on an annual basis (at the time of continuing review). The PI will be responsible for informing the IRB immediately of any life threatening incidents as well as take appropriate action to stop the study, release a participant from the study, or modify procedures to reduce and/or eliminate the occurrence of the risks.

The PI will review information on adverse events, protocol deviations, data quality, participant recruitment, accrual, and retention (including reasons for dropout), whether all participants met inclusion criteria, and demographics. This information will be provided in biannual reports to an Independent Monitor who will make recommendations regarding the safe continuation of the study and whether any changes to the protocol are needed to ensure participant safety. Once annually the Independent Monitor will forward an approved report to the UW Health Sciences IRB and NIMH.

Given the safety and risk level of the intervention and study procedures, we cannot anticipate any conditions that would trigger an immediate suspension of the research.

